9.4.5. Safety Analyses

All safety analyses will be made on the Safety Analysis Set.

Summaries for the safety parameters corresponding to the primary endpoints (including TEAEs and TESAEs) are described in Section 9.4.2 above. Additionally, listings will be provided for severe AEs, drug-related AEs, SAEs, and AEs leading to study discontinuation.

Descriptive statistics and changes from baseline at each assessment timepoint will be presented by treatment (or cohort) for the Clinic Period for:

- Clinical laboratory values (in standard units) for each hematology, chemistry, and urinalysis parameter
- Vital signs (ie, pulse rate, systolic and diastolic blood pressure, oral temperature, and body weight)
- ECG parameters
 - Additionally, the overall 12-lead ECG interpretation (normal, abnormal not clinically significant, or abnormal clinically significant) will be summarized.

9.4.6. Other Analysis/Analyses

Not applicable.

9.5. Interim Analyses

No interim analysis is planned for the study. Interim safety reviews are detailed in Section 6.6.

9.6. Data Monitoring Committee (DMC)

This study will not utilize a DMC. A Dose Escalation Committee will be utilized to review safety data for each cohort in order to make decisions about dose escalation, as described in Section [6.6](#).

10. SUPPORTING DOCUMENTATION AND OPERATIONAL CONSIDERATIONS

10.1. Appendix 1: Regulatory, Ethical, and Study Oversight Considerations

10.1.1. Regulatory and Ethical Considerations

This study will be conducted in accordance with the protocol and with the following:

- Consensus ethical principles derived from international guidelines including the Declaration of Helsinki and Council for International Organizations of Medical Sciences (CIOMS) International Ethical Guidelines
- Applicable ICH GCP Guidelines
- Applicable laws and regulations

The protocol, protocol amendments, ICF, IB, and other relevant documents (eg, advertisements) must be submitted to an IRB/IEC by the investigator and reviewed and approved by the IRB/IEC before the study is initiated.

Any amendments to the protocol will require IRB/IEC approval before implementation of changes made to the study design, except for changes necessary to eliminate an immediate hazard to study subjects.

The investigator will be responsible for the following:

- Providing written summaries of the status of the study to the IRB/IEC annually or more frequently in accordance with the requirements, policies, and procedures established by the IRB/IEC
- Notifying the IRB/IEC of SAEs or other significant safety findings as required by IRB/IEC procedures
- Providing oversight of the conduct of the study at the site and adherence to requirements of 21 CFR, ICH guidelines, the IRB/IEC, European regulation 536/2014 for clinical studies (if applicable), and all other applicable local regulations

10.1.2. Financial Disclosure

Investigators and subinvestigators will provide the sponsor with sufficient, accurate financial information as requested to allow the sponsor to submit complete and accurate financial certification or disclosure statements to the appropriate regulatory authorities. Investigators are responsible for providing information on financial interests during the course of the study and for 1 year after completion of the study.

10.1.3. Informed Consent Process

The investigator or his/her representative will explain the nature of the study to the subject or his/her legally authorized representative and answer all questions regarding the study.

Subjects must be informed that their participation is voluntary. Subjects or their legally authorized representative will be required to sign a statement of informed consent that meets the requirements of 21 CFR Part 50, local regulations, ICH guidelines, Health Insurance Portability and Accountability Act (HIPAA) requirements, where applicable, and the IRB/IEC or study center.

The medical record must include a statement that written informed consent was obtained before the subject was enrolled in the study and the date the written consent was obtained. The authorized person obtaining the informed consent must also sign the ICF.

Subjects must be reconsented to the most current version of the ICF(s) during their participation in the study.

A copy of the ICF(s) must be provided to the subject or the subject's legally authorized representative.

Subjects who are rescreened are required to sign a new ICF.

10.1.4. Data Protection

All parties will comply with all applicable laws, including laws regarding the implementation of organizational and technical measures to ensure protection of participant data.

Subjects will be assigned a unique identifier by the sponsor. Any subject records or datasets that are transferred to the sponsor will contain the identifier only; subject names or any information which would make the subject identifiable will not be transferred.

The subject must be informed that his/her personal study-related data will be used by the sponsor in accordance with local data protection laws. The level of disclosure must also be explained to the subject who will be required to give consent for their data to be used as described in the ICF.

The subject must be informed that his/her medical records may be examined by clinical quality assurance auditors or other authorized personnel appointed by the sponsor, by appropriate IRB/IEC members, and by inspectors from regulatory authorities.

10.1.5. Committee Structure

Key study personnel, including sponsor and CRO representatives, and their contact details will be provided prior to the Site Initiation Visit.

The safety of this study will be closely monitored on an ongoing basis by sponsor representatives. A Dose Escalation Committee composed of sponsor and CRO representatives will make decisions about dose escalation, as detailed in Section 6.6.

10.1.6. Dissemination of Clinical Study Data

The sponsor will make study results available through www.ClinicalTrials.gov, or other public registries, in accordance with applicable local laws and regulations.

10.1.7. Data Quality Assurance

All subject data relating to the study will be recorded on the eCRF unless transmitted to the sponsor or designee electronically (eg, laboratory data). The investigator is responsible for verifying that data entries are accurate and correct by electronically signing the eCRF.

The investigator must maintain accurate documentation (source data) that supports the information entered in the eCRF.

The investigator must permit study-related monitoring, audits, IRB/IEC review, and regulatory agency inspections and provide direct access to source data documents.

Monitoring details describing strategy (eg, risk-based initiatives in operations and quality such as Risk Management and Mitigation Strategies and Analytical Risk-Based Monitoring), methods, responsibilities, and requirements, including handling of noncompliance issues and monitoring techniques (central, remote, or on-site monitoring) are provided in the Monitoring Plan.

The sponsor or designee is responsible for the data management of this study including quality checking of the data.

The sponsor assumes accountability for actions delegated to other individuals (eg, CROs).

Study monitors will perform ongoing source data verification to confirm that data entered into the CRF by authorized site personnel are accurate, complete, and verifiable from source documents; that the safety and rights of subjects are being protected; and that the study is being conducted in accordance with the currently approved protocol and any other study agreements, ICH GCP, and all applicable regulatory requirements.

Records and documents, including signed ICFs, pertaining to the conduct of this study must be retained by the investigator for the longer of:

- 2 years after the last marketing authorization for the study drug has been approved or the sponsor has discontinued its research with respect to the study drug, or
- Such longer period as required by applicable US regulatory requirements or by US law

No records may be destroyed during the retention period without the written approval of the sponsor. No records may be transferred to another location or party without written notification to the sponsor.

10.1.8. Source Documents

Source documents provide evidence for the existence of the subject and substantiate the integrity of the data collected. Source documents are filed at the investigator's site.

Data reported on the CRF or entered in the eCRF that are transcribed from source documents must be consistent with the source documents or the discrepancies must be explained. The investigator may need to request previous medical records or transfer records, depending on the study.

Definition of what constitutes source data can be found in the Monitoring Plan.

Description of the use of the EDC system is documented in the Data Management Plan.

10.1.9. Study and Site Start and Closure

The first act of recruitment is the date of first subject consent and will be the study start date.

The sponsor designee reserves the right to close the study site or terminate the study at any time for any reason at the sole discretion of the sponsor. The study site will be closed upon study completion. A study site is considered closed when all required documents and study supplies have been collected and a study-site closure visit has been performed.

The investigator may initiate study-site closure at any time, provided there is reasonable cause and sufficient notice is given in advance of the intended termination.

Reasons for the early closure of a study site by the sponsor or investigator may include but are not limited to:

- Failure of the investigator to comply with the protocol, the requirements of the IRB/IEC or local health authorities, the sponsor's procedures, or GCP guidelines
- Inadequate recruitment of subjects by the investigator
- Discontinuation of further study intervention development

If the study is prematurely terminated or suspended, the sponsor shall promptly inform the investigator, the IEC/IRB, the regulatory authorities, and any CRO(s) used in the study of the reason for termination or suspension, as specified by the applicable regulatory requirements. The investigator shall promptly inform the subject and should ensure appropriate subject therapy and/or follow-up.

Study termination is also provided for in the clinical study agreement. If there is any conflict between the contract and this protocol, the contract will control as to termination rights.

10.1.10. Publication Policy

The results of this study may be published or presented at scientific meetings. The sponsor will comply with the requirements for publication of study results. Any publication of data from the study by the investigator will be subject to mutual agreement between the investigator and the Sponsor.

10.2. Appendix 2: Clinical Laboratory Tests

All protocol-required laboratory assessments, as defined below, must be conducted in accordance with the laboratory manual and the [Schedule of Activities](#).

- The tests detailed in [Table 2](#) will be performed by the local laboratory, with the exception of the point-of-care hemoccult tests and ESR which will be sent to an outside laboratory.
- Protocol-specific requirements for inclusion or exclusion of subjects are detailed in Section [5](#) of the protocol.
- Additional tests may be performed at any time during the study as determined necessary by the investigator or required by local regulations.
- The investigator may consider repeating a laboratory test for any subject who has an abnormal laboratory test result (eg, positive hemoccult test, out-of-range chemistry test, abnormal urine culture) at Discharge (Day 2). The decision to repeat a laboratory test would be based on the investigator's clinical judgment after discussion with the sponsor's medical monitor and depending on the clinical context.
- Pregnancy testing is not required, as women of childbearing potential are not eligible for the study (Section [5](#)).

Table 2: Protocol-Required Safety Laboratory Assessments

Laboratory Assessments	Parameters			
Hematology	Platelet count	RBC Indices: MCV MCH MCHC % Reticulocytes		WBC Count with Differential: Neutrophils Lymphocytes Monocytes Eosinophils Basophils
	RBC count			
	Hemoglobin			
	Hematocrit			
Clinical Chemistry ^a	Blood urea nitrogen (BUN)	Potassium	AST	Total and direct bilirubin
	Creatinine	Sodium	ALT	Total protein
	Glucose	Calcium	Alkaline phosphatase	Magnesium
	Chloride	Albumin	Bicarbonate	Phosphate
	Cholesterol	Uric acid		
Routine Urinalysis	
 Specific gravity pH, glucose, protein, blood, and ketones, by dipstick Microscopic examination (if blood or protein is abnormal) Urine culture (if urinary tract infection is suspected) 			
Inflammatory markers	
 ESR (analyzed at an outside laboratory) CRP 			
Hemoccult testing	Point-of-care hemoccult test			
Other Screening Tests	Alcohol and drug screen (to include at minimum: amphetamines, barbiturates, cocaine, opiates, cannabinoids, and benzodiazepines). Urine cotinine test SARS-CoV-2 testing (Screening and Check-in) HIV antibody and hepatitis panel (HBsAg, and HCV antibody)			

^a All events of ALT >3×upper limit of normal (ULN) and bilirubin >2×ULN (>35% direct bilirubin) or ALT >3×ULN and international normalized ratio (INR) >1.5, if INR measured which may indicate severe liver injury (possible Hy's Law), must be reported as an SAE (excluding studies of hepatic impairment or cirrhosis).

Investigators must document their review of each laboratory safety report.

Laboratory/analyte results that could unblind the study will not be reported to CRU staff or other blinded personnel until the study has been unblinded.

10.3. Appendix 3: Adverse Events: Definitions and Procedures for Recording, Evaluating, Follow-up, and Reporting

10.3.1. Definition of AE and TEAE

10.3.1.1. AE Definition

- An AE is any untoward medical occurrence in a patient or clinical study subject, temporally associated with the use of study intervention, whether or not considered related to the study intervention.
- NOTE: An AE can therefore be any unfavorable and unintended sign (including an abnormal laboratory finding), symptom, or disease (new or exacerbated) temporally associated with the use of study intervention.

10.3.1.2. TEAE Definition

- A TEAE is an event that emerges, or a pre-existing event that worsens, any time after the initiation of the first dosing of the investigational product.

10.3.1.3. Events Meeting the AE Definition

- Any abnormal laboratory test results (hematology, clinical chemistry, or urinalysis) or other safety assessments (eg, ECG, radiological scans, vital signs measurements), including those that worsen from baseline, considered clinically significant in the medical and scientific judgment of the investigator (ie, not related to progression of underlying disease).
- Exacerbation of a chronic or intermittent pre-existing condition including either an increase in frequency and/or intensity of the condition.
- New conditions detected or diagnosed after study intervention administration even though it may have been present before the start of the study.
- Signs, symptoms, or the clinical sequelae of a suspected drug-drug interaction.
- Signs, symptoms, or the clinical sequelae of a suspected overdose of either study intervention or a concomitant medication. Overdose per se will not be reported as an AE/SAE unless it is an intentional overdose taken with possible suicidal/self-harming intent. Such overdoses should be reported regardless of sequelae.
- Specific Situations
 - AEs that are secondary to other AEs: In general, AEs that are secondary to other AEs (eg, cascade events or clinical sequelae) should be identified by their primary cause, with the exception of severe or serious secondary events. If a medically significant secondary AE that is separated in time from the initiating event occurs, the event may be recorded as an independent event on the AE eCRF after consultation with the sponsor. All AEs should be recorded separately if it is not clear as to whether the events are associated.

- **Persistent AEs:** A persistent AE is one that extends continuously, without resolution, between subject evaluation time points. If the severity changes throughout the duration of the persistent AE, record the severity as it changes.
- **Recurrent AEs:** A recurrent AE is one that resolves between subject visits and subsequently recurs. Each recurrence of the AE should be recorded as a separate AE on the AE eCRF.

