2.3.1. Risk Assessment

Potential Risk of Clinical Significance	Summary of Data/Rationale for Risk	Mitigation Strategy
Study Intervention: IW-3300		
Potential for diarrhea and secondary dehydration	These are class effects of GC-C agonism or effects observed in nonclinical safety pharmacology and toxicology studies of IW-3300.	Intrarectal administration will likely decrease the risk of diarrhea and subsequent dehydration. The study design includes dose escalation to closely monitor subject safety and tolerability at each dose level before dosing with a higher dose; a Dose Escalation Committee will conduct blinded reviews of all the safety parameters of the dosing cohort through Discharge (Day 2) in order to make decisions regarding escalation to the next dose. Orthostatic vital sign measurements will be taken to evaluate the potential for volume depletion. The daily BM frequency and stool consistency will be monitored in real time to evaluate changes in bowel habits and the potential risk of diarrhea. Stopping rules will also be in place to evaluate continued dosing (Section 7.1.1); dosing within a cohort may be temporarily suspended in the event of a diarrhea or dehydration serious adverse event (SAE); ≥ 1 subject with Grade 3 diarrhea (increase from baseline of >7 stools per day and/or watery stools [BSFS score of 7] resulting in a limiting of self-care activities) or dehydration (hospitalization indicated); or ≥ 2 subjects with Grade 2 diarrhea (increase from baseline of 4 to 6 stools per day and/or watery stools [BSFS score of 7] resulting in a limiting of instrumental activities) or dehydration (intravenous fluids indicated).

Potential Risk of Clinical Significance	Summary of Data/Rationale for Risk	Mitigation Strategy

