7.1.1. Study Suspension or Termination

Dosing at a given dose level may be temporarily suspended if any of the following occur within a cohort:

- ≥ 1 subject with an SAE considered related to study drug
- ≥ 1 subject with a Common Terminology Criteria for Adverse Events (CTCAE) Grade 3 or higher AE considered related to study drug (CTCAE v5.0 will be used; grading criteria are summarized in Appendix 3/Section [10.3.3](#))
- ≥ 2 subjects with CTCAE Grade 2 or higher AEs considered related to study drug

The Dose Escalation Committee should consider the benefit-risk ratio in their determination to suspend dosing temporarily or permanently. If the benefit-risk is considered unacceptable and the effect is considered related to active study drug by the Dose Escalation Committee, dosing at a given dose level will be stopped, and no additional cohorts will be dosed at the same or higher dose level (a lower dose could still be studied).

The sponsor may permanently terminate the study, or a component of the study, at any time. Reasons for termination may include, but are not limited to:

- Death, SAE, or other safety finding considered to be related to IW-3300 that may preclude further dosing.

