10.3.2. Definition of SAE

If an event is not an AE per definition above (Section 10.3.1), then it cannot be an SAE even if serious conditions are met (eg, hospitalization for signs/symptoms of the disease under study, death due to progression of disease).

An SAE is defined as any untoward medical occurrence that, at any dose:

1. Results in death
2. Is life-threatening
 - The term “life-threatening” in the definition of “serious” refers to an event in which the subject was at risk of death at the time of the event. It does not refer to an event, which hypothetically might have caused death, if it were more severe.
3. Requires inpatient hospitalization or prolongation of existing hospitalization
 - In general, hospitalization signifies that the subject has been detained (usually involving at least an overnight stay) at the hospital or emergency ward for observation and/or treatment that would not have been appropriate in the physician's office or outpatient setting. Complications that occur during hospitalization are AEs. If a complication prolongs hospitalization or fulfills any other serious criteria, the event is serious. When in doubt as to whether “hospitalization” occurred or was necessary, the AE should be considered serious.

- Hospitalization for elective treatment of a pre-existing condition that did not worsen from baseline is not considered an AE.

4. Results in persistent disability/incapacity
 - The term disability means a substantial disruption of a person's ability to conduct normal life functions.
 - This definition is not intended to include experiences of relatively minor medical significance such as uncomplicated headache, nausea, vomiting, diarrhea, influenza, and accidental trauma (eg, sprained ankle) which may interfere with or prevent everyday life functions but do not constitute a substantial disruption.
5. Is a congenital anomaly/birth defect
6. Other situations:
 - Medical or scientific judgment should be exercised in deciding whether SAE reporting is appropriate in other situations such as important medical events that may not be immediately life-threatening or result in death or hospitalization but may jeopardize the subject or may require medical or surgical intervention to prevent one of the other outcomes listed in the [above](#) definition. These events should usually be considered serious.

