10.3.3.2. Assessment of Intensity/Severity

The investigator will make an assessment of intensity for each AE and SAE reported during the study and assign it to 1 of the following categories, according to the National Cancer Institute Common Terminology Criteria for Adverse Events [NCI-CTCAE]):

- Grade 1: Mild; asymptomatic or mild symptoms; clinical or diagnostic observations only; intervention not indicated.
- Grade 2: Moderate; minimal, local or noninvasive intervention indicated; limiting age-appropriate instrumental Activities of Daily Living (ADL).
- Grade 3: Severe or medically significant but not immediately life-threatening; hospitalization or prolongation of hospitalization indicated; disabling; limiting self care ADL.
- Grade 4: Life threatening consequences; urgent intervention indicated.
- Grade 5: Death related to AE.

A semicolon indicates “or” within the description of the grade.

ADL are defined as follows: Instrumental ADL refer to preparing meals, shopping for groceries or clothes, using the telephone, managing money, etc. Self care ADL refer to bathing, dressing and undressing, feeding self, using the toilet, taking medications, and not bedridden.

An event is defined as “serious” when it meets at least 1 of the predefined outcomes as described in the definition of an SAE, NOT when it is rated as severe.

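### The default rule for secondary AEs in protocol 10.3.1.3 can keep non-serious Grade 2 dehydration due to diarrhea out of the TEAE tables, although 2.3.1 names it as a study-drug risk

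*Protocol*

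**What the plan says.** **Recording rule.** Protocol 10.3.1.3 (Specific Situations) sets a general default: "AEs that are secondary to other AEs (eg, cascade events or clinical sequelae) should be identified by their primary cause". The default applies "with the exception of severe or serious secondary events". Two further provisions follow. If a secondary event is medically significant and separated in time from the initiating event, "the event may be recorded as an independent event on the AE eCRF after consultation with the sponsor". If it is unclear whether events are associated, each is recorded separately.

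**Named risk.** The first row of the risk table in 2.3.1 is headed "Potential for diarrhea and secondary dehydration". It gives dehydration its own criteria beside those for diarrhea: need for hospitalization at Grade 3 and, at Grade 2, "or dehydration (intravenous fluids indicated"). One subject at Grade 3, or two at Grade 2, may trigger temporary suspension. The general rule in 7.1.1 likewise counts two or more "subjects with CTCAE Grade 2 or higher AEs considered related to study drug".

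**Tables.** Protocol 9.4.2 summarizes TEAEs by system organ class and preferred term. SAP 7.1 adds tables by CTCAE grade and by relationship to study drug.

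**The concern.** Dehydration after diarrhea is a typical clinical sequela, and 2.3.1 itself calls it secondary. The general recording rule therefore catches the one secondary harm that the protocol singles out for this drug. Site staff have to recognize and grade Grade 2 dehydration for the suspension criteria, yet the recording rule lets them enter only diarrhea on the AE page.

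The TEAE tables count what is recorded under each preferred term. A first-in-human report could show an empty dehydration row at a dose where a subject needed intravenous fluids. Because the default holds only in general and its exceptions rest partly on judgment, like cases could also be recorded differently from one cohort to the next.

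**Working it through.** The plan states no figure to reproduce. The check is to take one case through each provision and then see which outputs move.

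**Test case:** dehydration needing intravenous fluids (Grade 2), non-serious, clearly caused by diarrhea, within the same episode.

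1. *Default, 10.3.1.3.* The event is secondary, so it is identified as diarrhea.
2. *Severe exception.* Section 10.3.3.2 equates severe with Grade 3, so Grade 2 is not excepted.
3. *Serious exception.* Section 10.3.2 says of important medical events: "These events should usually be considered serious". Some intravenous-fluid cases will leave the default this way, by judgment. The test case is one that does not.
4. *Separated in time.* This does not apply within one episode. Where it does apply, it is permissive and needs sponsor consultation.
5. *Unclear association.* This does not apply, because the cause is clear.
6. *Other sections.* Section 8.3.8 defines no adverse events of special interest. Section 10.3.3.1 prefers a diagnosis to individual signs and symptoms but does not address secondary dehydration. Section 2.3.1 covers suspension of dosing and is silent on AE records.

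No provision requires a separate dehydration record.

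**Size, by illustration.** Inputs: 6 active subjects per cohort (protocol 1.1.7). Assumptions: k = 1 subject with the test case, related to study drug, and no other TEAE at that dose level. Intervals are exact (Clopper-Pearson) 95%:

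- 0/6: upper limit = 1 − 0.025^(1/6) = 45.9%.
- 1/6: lower limit = 1 − 0.975^(1/6) = 0.4%. The upper limit solves (1−p)^6 + 6p(1−p)^5 = 0.025, giving 64.1%.

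| Output | Recorded separately | Recorded as diarrhea only |
|---|---|---|
| Dehydration row | 1/6 = 16.7% (0.4–64.1%) | 0/6 = 0% (0–45.9%) |
| Dehydration at Grade 2 | 1/6 | 0/6 |
| Any TEAE | 1/6 | 1/6 |
| TESAE | 0/6 | 0/6 |
| Subjects with related Grade 2+ AE (7.1.1) | 1 | 1, if graded correctly |

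For k = 1, 2 or 3 of 6, the row would read 16.7%, 33.3% or 50.0% against 0%. In pooled placebo (2 per cohort, 4 to 5 cohorts, so 8 to 10 subjects), one folded event removes 1/8 = 12.5% to 1/10 = 10.0%.

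**The last line of the table.** Section 10.3.3.2 limits Grade 1 to mild events, "clinical or diagnostic observations only; intervention not indicated". An episode for which intravenous fluids are indicated cannot correctly be Grade 1, so a diarrhea record that absorbs it should be at least Grade 2 and the subject is still counted. Section 2.3.1 also counts Grade 2 dehydration in its own right.

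**The case against.** The strongest reply is that the two sections can be read together. The default holds only in general, 2.3.1 is the study-specific text, and 7.1.1 counts AEs, so dehydration that counts toward suspension must have been recognized as an AE. This does not close the gap: 2.3.1 governs whether dosing continues, and neither section says that dehydration gets its own AE record.

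Several other replies stand, and they limit the point.

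- *The group is narrow.* The event must be non-serious, below Grade 3, clearly due to diarrhea, and not recorded separately at discretion. The protocol also expects the rectal route to reduce both harms.
- *Volume depletion is not hidden.* SAP 7.2 and 7.3 tabulate flagged laboratory, weight, vital-sign and orthostatic values by treatment group, whatever the AE coding. Those tables show markers, however, and their thresholds are wide (for example, a weight loss of at least 7%, or creatinine above 1.3 times the upper limit of normal). They do not give a graded dehydration incidence by dose.
- *The default has a purpose.* It avoids counting one episode under two terms.
- *The counts are assumed.* The contrast of 16.7% with 0% shows what one unrecorded event does; it does not show how likely that event is.

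A reader might infer that Grade 1 dehydration raises the same conflict. The documents do not support that: 2.3.1 gives dehydration criteria only for Grades 2 and 3, and recording mild dehydration under its cause is a defensible convention.

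**Conclusion.** The point holds at Grade 2. As written, 10.3.1.3 does not require a separate record for non-serious Grade 2 dehydration clearly due to diarrhea, so one preferred-term row and its grade can be too low for a harm that 2.3.1 names. At 6 active subjects per dose level, each such event shifts that row by 16.7 percentage points. Whether any will occur cannot be judged from the documents.

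A reader might go further and infer that the primary endpoints as a whole are biased, or that a suspension trigger could be missed. Neither follows. A subject with folded dehydration still has a recorded TEAE, and serious or Grade 3 and higher events are excepted from the default. The 7.1.1 count stays the same provided the diarrhea record is graded correctly. That condition matters somewhat, because the Grade 2 diarrhea criteria in 2.3.1 do not mention intravenous fluids and staff would have to rely on the general grade definitions. Severity is low.

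**What to change.** In 10.3.1.3, extend the exception for severe or serious secondary events by adding: *and dehydration of CTCAE Grade 2 or higher secondary to diarrhea, which is always recorded as a separate AE with its own CTCAE grade.* Recording Grade 1 separately is optional.

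The cost is one clause in the protocol. It needs no new data, procedure or analysis, and SAP 7.1 would tabulate the event without change. The small downside is that one clinical episode may appear under two preferred terms; subject-level any-TEAE incidence stays the same.
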